10.9.2.1. Severity

Severity describes the intensity of an event, and will be assessed as:

Mild

The AE is easily tolerated and does not interfere with daily activity.

Moderate

The AE interferes with daily activity, but the subject is still able to function. Medical intervention may be considered.

Severe

The AE is incapacitating and requires medical intervention.

If an AE changes in severity, it should be reported as an AE of new severity but with the same description.

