5.3. Study Endpoints

5.3.1. Primary Endpoints

Number of AEs, SAEs, adverse drug reactions (ADRs), and AEs leading to treatment discontinuation.

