6. INVESTIGATIONAL PLAN

6.1. Overall Study Design

Subjects with aPAP who have completed the IMPALA (MOL-PAP-002) trial will be eligible for this trial.

At the Baseline visit, eligible subjects may continue or re-start treatment with inhaled molgramostim (300 µg) administered intermittently in cycles of seven days molgramostim, administered once daily, and seven days off treatment.

Trial visits will be conducted at 6-monthly intervals until the end of trial. Participating subjects will be encouraged to contact the clinic between visits if they experience AEs or worsening of aPAP, or if they have any other concerns.

During the trial, WLL will be applied as rescue therapy. The criterion for performing WLL is clinical worsening of aPAP based on symptoms, reduced exercise capacity and/or findings of hypoxemia or desaturation according to the investigator's judgement. The reason(s) for conducting WLL will be documented. Subjects undergoing WLL will continue treatment with molgramostim, unless discontinuation is medically required, according to investigator's discretion.

Subjects may discontinue molgramostim due to remission of aPAP, lack of response that requires a different treatment modality, or AEs. Subjects becoming pregnant will be required to discontinue treatment with molgramostim. Subjects who discontinue molgramostim will continue in the trial and attend visits according to the same schedule until end of the trial. Molgramostim treatment may be re-started if medically required. Subjects not requiring treatment at the Baseline visit may start molgramostim treatment during the trial if medically required.

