10.3. Medical History

Medical history assessment will be assessed at Baseline (Visit 1).

AEs that occurred during previous treatment with inhaled molgramostim, were reported as AEs in IMPALA, and are still ongoing, will be recorded as medical history. AEs that occurred after completion of IMPALA but still had a reasonable time-relationship to inhaled molgramostim treatment, and were not reported in IMPALA, and are still ongoing, will be reported as AEs at Baseline (Visit 1).

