7.1 Analysis and Presentation of the Primary Endpoint

All adverse events (AEs) occurring after informed consent will be reported in the eCRF. AEs will be coded using the Medical Dictionary for Regulatory Activities (MedDRA) version 21.0.

Events judged by the investigator to be related (including all events that are judged to be possibly related or probably related) to trial treatment are defined as adverse drug reactions (ADRs).

The primary endpoints are

- Adverse events (AEs)
- Serious adverse events (SAEs)
- Non-serious adverse events
- Adverse drug reactions (ADRs)
- Adverse events leading to treatment discontinuation

Adverse events leading to treatment discontinuation are defined as events where action taken with trial drug is marked as *Drug withdrawn in the eCRF*.

All the above adverse events will be summarized by system organ class (SOC) and preferred term (PT), and overall.

The overall summary will include AEs, serious AEs, non-serious AEs, ADRs, AEs leading to treatment discontinuation, fatal AEs and AEs by severity, AEs by action with trial treatment, AEs by outcome.

The summaries by SOC and PT will include number of events, number of subjects, proportion of subjects reporting these events, and rate of events. For each of the primary endpoints, summaries will be given by severity, relationship to trial drug, and outcome.

A summary of treatment emergent adverse events by preferred term with frequency $\geq 5\%$ will be provided together with a summary of treatment emergent non-serious adverse events by preferred term with frequency $\geq 5\%$.

Patient listings corresponding to the summaries, will be provided.

In summaries of adverse events by SOC and PT the tables will be sorted first by SOC and then by PT based on the frequency in the total column.

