8.1.1 Analysis and Presentation of Safety Parameters

8.1.2 Adverse Events

All adverse events (AEs) occurring after informed consent will be reported in the eCRF. AEs will be coded using the Medical Dictionary for Regulatory Activities (MedDRA) version 21.0.

Adverse events are considered treatment emergent if the onset of the events is on or after the first exposure date of IMP in this trial and until (estimated) last drug date + 7 days. Last drug date is defined as last kit date + 21 days or end of trial date whatever comes first. Only treatment emergent events will be included in the safety summaries.

Possible or probable related AE's are defined as ADRs.

Adverse events will be presented as described in section 7.1.

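### Severity-change entries can make one adverse event episode count more than once, and the onset-only treatment-emergence rule misplaces some pre-dose events (minor)

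*Protocol*

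**What the plan says.** Protocol 5.3.1 sets the primary endpoint as a count: "Number of AEs, SAEs, adverse drug reactions (ADRs), and AEs leading to treatment discontinuation". Protocol 10.9.2 has every AE record carry its own description, start and stop dates, severity, action taken, causality, seriousness and outcome. Protocol 10.9.2.1 adds: "If an AE changes in severity, it should be reported as an AE of new severity but with the same description".

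SAP 7.1 turns these records into the primary result: "The summaries by SOC and PT will include number of events, number of subjects, proportion of subjects reporting these events, and rate of events". It continues: "For each of the primary endpoints, summaries will be given by severity, relationship to trial drug, and outcome". Serious and non-serious events have separate tables (14.3.1.7 and 14.3.1.11).

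SAP 8.1.2 classes AEs as "treatment emergent if the onset of the events is on or after the first exposure date of IMP in this trial", with the window closing seven days after the estimated last drug date. It then states: "Only treatment emergent events will be included in the safety summaries".

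Neither document joins successive entries of one episode, gives a worst-severity rule, or says which start date a severity-change entry carries. Two sentences come close but deal with other matters. The grouping instruction in Protocol 10.9.2 concerns related signs and symptoms, and the linking instruction in Protocol 10.9.3.1 concerns SAE follow-up forms.

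**The concern.** The recording rule works at the level of a severity phase, while a reader of the primary tables will probably take an event to be an episode. If each phase is an entry and entries are counted, event numbers and rates can exceed the number of episodes. Entries of one episode can also scatter over severity and outcome rows, and over the serious and non-serious tables. The outcome list in Protocol 10.9.2.3 has no category for an entry closed only because severity changed.

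The onset-only rule raises a second problem. Whether a pre-dose event enters the safety summaries depends on an unstated dating convention, and neither convention separates improvement from worsening on drug.

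The counts are the primary result. By SAP 3.2 they feed the continuing safety evaluation and a possible marketing application, and by Protocol 11 the data are to be combined with IMPALA.

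**Working it through.** The plan gives no figure to reproduce: Protocol 11 states that there was no formal sample size calculation, and no expected number of AEs is given. The check is a count under the stated rules.

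**1. One episode, all on drug, possibly related.** It runs mild and non-serious, then severe and serious, then mild and non-serious. The entries come from the Protocol 10.9.2.1 rule read as creating records, and the counts from SAP 7.1.

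| | Counted by entry | Joined |
|---|---|---|
| AEs | 3 | 1 |
| ADRs | 3 | 1 |
| SAEs | 1 | 1 |
| Non-serious AEs | 2 | 0 |
| Severity categories filled | 2 | 1 |
| Subjects | 1 | 1 |

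The result is the same whether the later entries are dated at the change or at the original onset, because all dates lie inside the window.

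**2. Effect on totals.** Let f be the share of episodes that change severity and m the number of changes in each. Both are assumptions; the documents give neither.

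Counted events per 100 episodes = 100 × (1 + f × m)

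| f | m = 1 | m = 2 |
|---|---|---|
| 5% | 100 × 1.05 = 105 | 100 × 1.10 = 110 |
| 10% | 100 × 1.10 = 110 | 100 × 1.20 = 120 |
| 20% | 100 × 1.20 = 120 | 100 × 1.40 = 140 |

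For a fixed denominator, event rates rise by the same factor. The lower part of the range may be nearer the truth. Visits are six-monthly (Protocol 6.1), the diary items do not ask for severity (Protocol 10.5), and the routine question asks about new or worsening problems rather than improvement (Protocol 10.9.2).

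**3. Treatment emergence for events that begin before the first dose.** The SAP 8.1.2 rule is applied under each possible dating and compared with a rule based on starting or worsening.

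| Episode | Dated at change | Original onset kept | Starts-or-worsens rule |
|---|---|---|---|
| Moderate before dose, mild on drug | 1 | 0 | 0 |
| Mild before dose, severe on drug | 1 | 0 | 1 |
| Both | 2 | 0 | 1 |

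Dating at the change wrongly admits the event that only improves. Keeping the original onset wrongly leaves out the event that worsens. If Protocol 10.9.2.1 means updating the record, the onset stays before the first dose and the second error remains.

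**4. Who can have a pre-dose AE.** Events reported in IMPALA and still ongoing go to medical history. Those arising after IMPALA, plausibly related in time to the drug, unreported there and still ongoing, are recorded as AEs at Baseline (Protocol 10.3). The other source is late starters: "Subjects not requiring treatment at the Baseline visit may start molgramostim treatment during the trial if medically required". Where treatment starts at Baseline, the first dose is given at that visit (Protocol 9.5), which leaves little pre-dose time.

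**The case against.** The strongest reply is that recording and counting already agree: the protocol calls the new phase an AE, the endpoint is a number of AEs, and the SAP counts them. No entry is counted twice, and choosing the episode as the unit is a preference. That is fair as logic, but the SAP should then say that its events are entries, because the serious/non-serious split and the outcome tables are hard to read otherwise.

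The severity sentence may also mean updating the existing record, in which case no multiple counting arises. The documents do not settle this. The reference to an unchanged description fits a further entry better, but the alternative stands as a possibility.

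On onset, a new AE would ordinarily start when the new severity starts. Worsening on drug would then be captured, and only pre-dose events that improve would be misplaced. That narrows the point without removing it. The Safety Management Plan (Protocol 10.9.3.6) and the Data Management Plan (Protocol 14.1) are not in the documents and may hold a recording convention. How entries become counted events in the primary endpoint still belongs in the SAP.

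A reader might infer three stronger things:
- **That the trial's AE totals are inflated by a known amount.** The documents give no number of severity changes, so they do not support this.
- **That the number or proportion of subjects with AEs is overstated.** On the ordinary reading each subject counts once, although one subject can fill several severity or outcome rows.
- **That any change of severity puts an episode in both the serious and non-serious tables.** This needs entries that differ in seriousness, and Protocol 10.9.1.2 defines seriousness by consequences such as death or hospitalisation, not by severity grade.

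**Conclusion.** The point holds and is minor. If a severity change creates a further entry, SAP 7.1 counts entries, and one episode can appear several times in the event numbers and rates and across the breakdowns. The range of 105 to 140 events per 100 episodes rests wholly on assumed values (5% to 20% of episodes, one or two changes each); the actual size is unknown and may be small.

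The onset-only rule in SAP 8.1.2 misclasses one kind of pre-dose event under either dating, but few events can take that route. Numbers of subjects are largely unaffected, individual entries remain visible in Listing 16.2.7.1, and SAP 7.5 confirms that no test depends on the counts. The documents do not support a claim that the safety conclusions are unreliable.

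**What to change.** State the following in SAP 7.1 and 8.1.2 before database lock, for event counts and rates:

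- Join contiguous or overlapping entries of the same subject with the same reported description (verbatim term, confirmed by the same preferred term) into one event.
- Flag the event as treatment-emergent if it starts or worsens within the 8.1.2 window, not if it only improves.
- Take maximum severity, seriousness, strongest causality and *Drug withdrawn* only from entries within the window. For a pre-dose event, take them from the worsening entry onward. Do not carry in a worsening that begins more than seven days after the last drug date; unrestricted joining would turn a mild on-drug event into a severe or serious treatment-emergent one.
- Rank causality as probable, possible, unlikely, with *Not applicable* lowest.
- Take the outcome from the last entry.
- Date the change by the entry's start date or, if that repeats the original onset, by the earlier entry's stop date.
- Keep all individual entries in Listing 16.2.7.1 and report the entry-level count alongside.

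The cost is a few sentences and a small derivation from fields already collected under Protocol 10.9.2, plus possible site queries where a change has no usable date. Because the rule works on existing fields, it needs no new instruction to sites, which matters because SAP version 3.0 is dated January 2021 and treatment was to run only to the end of 2020. The downside is that event counts fall slightly and some distinct back-to-back episodes with the same description are joined; the entry-level count shows how much difference the joining makes.

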10.9.2.2. Relationship to Study Drug

An Investigator who is qualified in medicine must make the determination of relationship to the investigational product for each AE. Causality will be assessed as:

Probable

A clinical event, including laboratory test abnormality, with a reasonable time sequence to administration of the IMP, unlikely to be attributed to concurrent disease or other drugs or chemicals, and which follows a clinically reasonable response on withdrawal (dechallenge). Rechallenge information is not required to fulfil this definition.

Possible

A clinical event, including laboratory test abnormality, with a reasonable time sequence to administration of the IMP, but which could also be explained by concurrent disease or other drugs or chemicals. Information on IMP withdrawal may be lacking or unclear.

Unlikely

A clinical event, including laboratory test abnormality, with a temporal relationship to IMP administration which makes a causal relationship improbable, and in which other drugs, chemicals or underlying disease provide plausible explanations.

Not applicable

This assessment can be used e.g. in cases where the subject did not receive any treatment with IMP or if the causality cannot be judged because information is insufficient or contradictory.

10.9.2.3. Outcome

The outcome of AEs has to be described by following criteria:

- Recovered
- Not Recovered
- Recovered with sequelae
- Fatal
- Unknown.

10.9.2.4. Follow-up of Subjects after Adverse Events

Any AE that is ongoing when the subject is withdrawn from the trial should be followed-up until the AE is resolved or the investigator decides that the AE is stable and needs no further follow-up.

10.9.2.5. Abnormal Laboratory Values/Vital Signs

An asymptomatic abnormal laboratory/vital sign finding should only be reported as an AE if it is clinically significant according to the investigator's assessment, if it fulfils the criteria for an SAE or if it causes the subject to discontinue the trial.

If an abnormal laboratory/vital sign value is associated with clinical signs and symptoms, the sign/symptom should be reported as an AE and the associated laboratory/vital sign result should be considered additional information.

10.9.3. Reporting Adverse Events

10.9.3.1. Serious Adverse Event (SAE) Reporting Procedure

The investigator is responsible for ensuring that all SAEs are reported to the sponsor immediately, using a trial-specific SAE form, but in any event no later than 24 hours of any site staff becoming aware of the event from the time the informed consent has been signed, up to Day 30 after the last visit. Reporting of SAEs will also be described in a trial-specific procedure.

After that period of time only serious adverse reactions (events related to trial medication) have to be reported. SAEs occurring to a patient after the patient has completed the clinical trial and for which a reasonable possibility of a causal relationship is assessed by the Investigator, must be reported by the Investigator to Premier Research regardless of the time that has elapsed (post-trial events). The SAE form has to be completed in English.

Initial reports should be followed as soon as possible by detailed written reports. The initial and follow-up reports should identify subjects by unique code numbers assigned in the trial. The subjects' names, personal identification numbers, and/or addresses must not be included. The following information is **mandatory** for the initial report:

- Subject trial ID
- Trial treatment (blinded, if applicable)
- Start date (time, if relevant) of the trial treatment
- Brief description of the event (diagnosis)
- Start date (time, if relevant) of the event
- Seriousness criteria
- Causality assessment.

For reported deaths, the investigator should supply the sponsor and the IEC/IRB (if applicable) with any additional requested information (e.g. autopsy reports and terminal medical reports).

The Investigator must contact Premier Research by email or fax directly to Premier Research Pharmacovigilance and Device Safety in case of all SAEs **within 24 hours after awareness of the event**.

SAE REPORTING CONTACT DETAILS

Company: Premier Research

Department: Pharmacovigilance and Device Safety (PVDS)

E-mail: [contact]

[contact]

Note: If there is local legislation requiring investigators to report AEs to the Competent Authority or the IEC/IRB, the investigator should also comply with this legislation. If any such reporting is planned, this must be stated in the SAE report, and once the reporting has been performed, a copy of the reporting documentation must be enclosed with the SAE-Follow-Up report to the sponsor.

The initial SAE report should be completed by the investigator immediately, even if not all data are available. Relevant follow-up information must be faxed or sent by e-mail to Premier PVDS as soon as possible. SAE-Follow-Up reports also have to be recorded on the trial specific SAE form. A follow-up report should be clearly marked as such and linked to the initial report.

The medical term of the SAE should be an event, reaction or diagnosis rather than a list of symptoms. It is important to enter the most appropriate event term in the corresponding field.

The Investigator should complete all the details requested including dates of onset, severity, corrective therapies given, outcome and his/her opinion as to whether the reported event is possibly drug-related.

In the case of death of a trial patient, the Investigator has to provide any additional information necessary as requested by the sponsor, the Competent Authorities concerned and IEC/IRBs concerned.

10.9.3.2. Suspected Unexpected Serious Adverse Reaction (SUSAR) Reporting Procedure

According to national legislation and European directives and guidelines, the sponsor of the clinical trial will report all SUSARs to the Competent Authority and IEC/IRB in all Member States concerned, to the European clinical trials database (Eudravigilance Clinical Trial Module - EVTCM), and if applicable, to other regulatory authorities according to local laws and regulations.

The Sponsor shall ensure that all relevant information about SUSARs that are fatal or life-threatening is recorded and reported as soon as possible to the Competent Authorities in all the Member States concerned, and to IEC/IRB (if required by local regulations), and in any case no later than seven days after knowledge by the Sponsor of such a case, and that relevant follow-up information is subsequently communicated within an additional eight days.

Any other SUSARs shall be reported to the Competent Authorities concerned and to the IEC/IRB concerned as soon as possible but within a maximum of 15 days of first knowledge by the sponsor.

The investigator should be aware of local reporting regulations to the IEC/IRB. The Sponsor will either supply the investigator with the reports which should be passed on to the IEC/IRB or report directly to the IEC/IRB depending on local regulations.

10.9.3.3. Adverse Events of Special Interest

There are currently no AEs of special interest identified due to limited previous experience of Savara's molgramostim.

10.9.3.4. Precautions/Overdose

No acute systemic or hypersensitivity reactions have been reported in subjects receiving inhaled sargramostim or molgramostim products.

There is no known antidote to molgramostim. In the event of overdose, symptomatic management is indicated.

Based on information from similar products, overdose may manifest with respiratory symptoms, e.g. bronchospasm, wheezing, dyspnoea, decreased pulmonary function or cough.

Haematologic findings such as leukocytosis and neutrophilia may occur if overdose results in high systemic exposure. With high systemic doses of similar products, the following symptoms have been observed: tachycardia, hypotension, dyspnoea, and flu-like symptoms. These symptoms abated quickly on symptomatic treatment. More information is available in the IB.

10.9.3.5. Pregnancy

Female subjects will be instructed to notify the investigator immediately if they become pregnant during the trial. Male subjects will be instructed to notify the investigator immediately if their female partner becomes pregnant. Pregnant subjects will be withdrawn from further trial treatment. The subjects will also be instructed to report pregnancies discovered after the last visit, if they believe that conception occurred during their participation in the trial.

A pregnancy as such is not an AE, unless there is a possibility that the IMP has interfered with the efficiency of any contraceptive measures. However, the investigator should report pregnancies according to the procedures and timelines described for reporting of SAEs, Section 10.9.3.1. The pregnancy report form should be used instead of the SAE form.

The pregnant subject or partner will be followed until the end of the pregnancy. Any complication during the pregnancy should preferably be reported as an AE. The outcome of the pregnancy must be reported on the pregnancy report form. Any spontaneous abortion, stillbirth, birth defect/congenital anomaly, death, or other serious infant condition must be reported and followed up as an SAE.

